### **3. Treatment Protocol in Emergency Situations:**

In cases of medical emergencies requiring unblinding for patient care, investigators will be allowed access to the donor allocation. Donor allocation should remain blinded unless necessary to ensure the participant's urgent medical care. The rationale for unblinding, along with the date and details of the unblinding, must be clearly documented. All participants will undergo follow-up by week 6 unless they explicitly decline.

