### **3. Results:**

1.Primary Outcome: The primary outcome is a composite of steroid-free clinical remission

together with endoscopic remission or response at week 12, defined as a total Mayo score of  $\leq 2$  points with no individual sub-score  $>1$  point, and at least a 1 point reduction from baseline in the endoscopy sub-score (MES).

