## 4. Methods:

**1. Study Design:** This is a patient single-blind, single-center, randomized, parallel-group pilot clinical trial without placebo control. Patients will be randomized to either the Han donor or the Bai donor and followed up for a 12-week period. Subjects will undergo follow-up assessments for up to 12 weeks in accordance with the same schedule as the blinded phase (i.e., FMT administration at baseline, weekly telephone follow-up at week 1, 8, and on-site follow-up visits at week 12). Subjects who are randomized to the FMT arm or who do not wish to enter the open-label phase will be deemed to have completed the study, and no further follow-up will be arranged.

Note: Single-center means all experimental activities are conducted at the same location.

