### **2. Treatment and Follow-Up (Week 0 to Week 12)**

Participants will undergo two colonoscopies with biopsies performed at two time points: before treatment, at 8 – 12 weeks post-FMT

Stool samples will be collected at the following times: before treatment, at the end of FMT treatment, 8 weeks post-FMT, 12 weeks post-FMT.

During each visit, Mayo scores (including endoscopic subscoring) were evaluated by blinded outcome assessors. Biopsies were performed for histological assessments, and histological scoring was conducted by a blind pathologist. A dedicated telephone line was available for patients to report any adverse events or worsening of symptoms between scheduled visits. All investigators were aware of group allocation, while endoscopists, pathologists, and outcome assessors remained fully blinded to group assignments to minimize assessment bias.

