#### 11. Statistical Analysis

Continuous variables will be expressed as means (SD) and compared between groups using unpaired t-tests. Categorical variables will be compared using the chi-square test or Fisher's exact test. A modified intent-to-treat analysis will include all participants who have received at least one FMT treatment. Participants requiring additional treatment, violating the study protocol, failing to discontinue corticosteroids by week 12, or discontinuing the study for any reason will be considered treatment failures. Per-protocol analysis will include participants who completed the 12-week blind treatment course without protocol violations. Missing data were handled using complete-case analysis in the primary analysis. A two-sided p-value of <0.05 will be considered statistically significant. Safety data will be summarized using descriptive statistics. All statistical analyses will be performed using R (4.0.5).

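### The emergency-unblinding section sets a week-6 follow-up that fits no other schedule in the plan and conflicts with the week-12 primary outcome

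*Combined protocol and SAP*

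**What the plan says.** Section 7, item 3 (Treatment Protocol in Emergency Situations) lets investigators look up the donor allocation when urgent care requires it, asks for the reason and date to be recorded, and then says: "All participants will undergo follow-up by week 6 unless they explicitly decline".

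The rest of the plan runs on a different clock:

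- Section 4, item 1 (Study Design), on duration: "Patients will be randomized to either the Han donor or the Bai donor and followed up for a 12-week period".
- The same item, on contacts: "FMT administration at baseline, weekly telephone follow-up at week 1, 8, and on-site follow-up visits at week 12".
- Section 3, on the primary outcome: steroid-free clinical remission "together with endoscopic remission or response at week 12".
- Section 5, Treatment and Follow-Up, on colonoscopies with biopsy: "before treatment, at 8 – 12 weeks post-FMT".
- The same section, on stool samples: "before treatment, at the end of FMT treatment, 8 weeks post-FMT, 12 weeks post-FMT".

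Section 11 has two rules that could apply to a participant without a week-12 result. One counts additional treatment, protocol violation or leaving the study for any reason as treatment failure. The other reads "Missing data were handled using complete-case analysis in the primary analysis".

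**The concern.** The week-6 sentence is current operative text, and it is the only follow-up instruction in the section that staff would consult after an emergency unblinding. Nothing there says that the participant continues to week 12. Section 4 does give such an assurance to users of prohibited medication, who stay enrolled and are still evaluated. Unblinded participants have no equivalent statement.

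What is at stake is whether the primary outcome is captured. Someone last assessed at week 6 has had no post-treatment colonoscopy, so the endoscopic part of the composite cannot be scored. How that person enters the primary comparison would then depend on which of the two rules in section 11 the analyst applies.

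**Working it through.** This is a comparison of times. The plan offers no figure to reproduce on this point: the sample size (50 + 50 = 100) is stated without derivation, and no rate of emergency unblinding is given.

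**Step 1. Compare week 6 with every stated time.**

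| Item | Time in the plan | Where | Relation to week 6 |
|---|---|---|---|
| Planned contacts | baseline, weeks 1, 8, 12 | Section 4, item 1 | none at week 6 |
| Stool samples | before and at end of FMT, weeks 8, 12 | Section 5 | none at week 6 |
| Second colonoscopy | weeks 8 to 12 | Section 5 | 8 − 6 = 2 to 12 − 6 = 6 weeks later |
| Primary outcome | week 12 | Section 3 | 12 − 6 = 6 weeks later |
| Length of follow-up | 12 weeks | Section 4, item 1 | 12 − 6 = 6 weeks longer |

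Week 6 matches nothing and precedes every post-treatment endoscopic assessment.

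**Step 2. Set out what the sentence can mean.**

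- *A contact no later than week 6.* No primary outcome is lost. The sentence is then either already met by the week-1 call or asks for a week-6 contact that no schedule contains.
- *Follow-up through week 6, for all participants.* This is the literal scope. It would cover all 100 enrolled and leave no one with a primary endpoint, so it cannot be squared with sections 3 to 5.
- *Follow-up through week 6, for unblinded participants only.* The section title suggests this scope, but the sentence does not state it. The number is unknown.

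**Step 3. Consequence for the endpoint under either through-week-6 reading.** The primary outcome needs a drop of at least 1 point in the endoscopy sub-score. That needs a second colonoscopy, and the earliest is at week 8. With follow-up stopped at week 6, the outcome is unobserved.

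**Step 4. Consequence for the analysis.** Take an arm with n treated participants, s successes and m participants without a week-12 assessment:

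- treatment-failure rule: success rate = s / n
- complete-case rule: success rate = s / (n − m)

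When s and m are both above zero, the second rate is higher. The plan does not say which rule takes precedence. It is also arguable whether the failure rule applies at all to someone who needed no additional treatment and whose assessments stopped because the protocol said so, since that person neither left the study nor violated the protocol. No value of m can be taken from the documents, so I give no numerical shift.

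**The case against.** The strongest reply is that this is a stray number. Sections 3, 4 and 5 agree on a 12-week course, the Groups table in section 5 counts patients who complete 12 weeks, and section 11 refers to a 12-week course. Section 4, item 1 also mentions an open-label phase that the design does not otherwise describe, so text carried over from another protocol is plausible. A sensible site would keep to week 12. That may well be the explanation, but it does not remove the contradiction, because the sentence remains an instruction.

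A reader might go further and infer that follow-up ends at week 6 for emergency cases, that these likely failures drop out of the analysis, and that success rates therefore rise, unequally if emergencies differ by donor. The documents do not support that chain:

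- The sentence does not say that follow-up ends, and no section says that unblinded participants leave the study or skip week 12.
- It refers to all participants, so selective loss of emergency cases is not what it literally describes.
- Section 11 counts additional treatment, or leaving the study for any reason, as failure. Many emergency cases could be kept as failures, so dropping them is only one possible result.
- The modified intent-to-treat set takes in everyone who received a transplant and has no exclusion for unblinding.
- Nothing in the plan indicates how often emergencies occur or whether they would differ by donor.

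It is also tempting to subtract a few cases from the 30 per arm in the Groups table. That does not work: those 30 are defined as having completed 12 weeks, so someone lost at week 6 was never among them.

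The tension between the two rules in section 11 affects all missing data and is not caused by the week-6 sentence. It matters here because it leaves the consequence open.

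**Conclusion.** The inconsistency is real and verifiable from the text. Week 6 is not a scheduled time; it falls 2 weeks before the earliest post-treatment colonoscopy and 6 weeks before the primary outcome. Loss of the primary outcome is conditional: it follows only if the sentence is read as follow-up through week 6. The participants covered would then be either treatment failures or missing, and the plan does not settle which.

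The size cannot be computed. Depending on the reading, the number affected runs from none, through an unknown number of unblinded participants, to all 100. No claim about bias between donor groups can be made from the documents. The point deserves correction because it touches capture of the primary outcome and costs almost nothing to settle.

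**What to change.** Reconcile section 7, item 3 with sections 3, 4 and 5:

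- Replace the week-6 sentence with a statement that all participants, including those unblinded in an emergency, remain in scheduled outcome follow-up through the week-12 primary assessment unless they decline.
- In section 11, state that participants without a week-12 assessment are handled by the treatment-failure rule, and that this takes precedence over the complete-case sentence for the primary outcome.

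This concerns outcome assessment and analysis only and leaves emergency care untouched. The cost is one sentence in each section. No visit, procedure or sample is added, because the week-12 visit is already planned. The wording should be settled before outcome data are examined.

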## **8. Research Samples**

### **1. Sample Collection and Storage**

All samples will be stored at -80 °C.

### **2. Sample Analysis**

#### **Fecal Calprotectin**

Once sufficient fecal samples are collected, QUANTA Lite calprotectin ELISA will be used to measure fecal calprotectin concentrations in batches. This is an enzyme-linked immunosorbent assay (ELISA) system based on a colorimetric detection of polyclonal antibodies to calprotectin. The ELISA range is 10 – 1800 mg/g, requiring a sample volume of 50 – 150 mL. The assay sensitivity is less than 10 mg/g. Analysis of the treatment arms will be performed in a blinded manner.

#### **Microbial Analysis**

##### **(1) Nucleic Acid Extraction**

According to the protocol, DNA will be extracted from the study samples using the Maxwell® RSC PureFood GMO and Authentication Kit. Fecal pellets will first be mixed with CTAB buffer and vortexed, followed by heating for 5 minutes. Proteinase K and RNase A will then be added to the sample, which will be incubated at 70 °C. After centrifugation, the supernatant will be collected and transferred to the Maxwell® RSC instrument for further processing.

##### **(2) Microbiome and Metabolomics Analysis**

Collected specimens will undergo laboratory microbial analysis, including the identification of bacterial, viral, and fungal components in the human microbiome. DNA will be enriched and extracted using different kits, such as the Qiagen QIAamp® DNA Mini Kit, Qiagen QIAamp DNA Stool Mini Kit, Mobio UltraClean® Tissue & Cells DNA Isolation Kit, and Maxwell® RSC PureFood GMO and Authentication Kit. Subsequent metagenomic sequencing will be performed

using the Novoseq 6000 system (2x300 bp paired-end reads). Bacterial, fungal, and viral analyses will be conducted using methplan2, UNITE2-Bowtie2, and Kraken2, respectively. To compare differences in microbiome, metabolome, and meta transcriptome configurations among treatment groups, donors, and specimens at different time points, statistical tools such as DESeq, Random Forest, LEfSe linear discriminant analysis and MasSlin2 will be used. DESeq and Random Forest will be executed in R, while Lefse analysis will be performed on the Huttenhower Lab Galaxy server (<http://huttenhower.sph.harvard.edu/>). DB-RDA analysis in R will describe the effects of clinical factors on multivariate datasets.

#### Animal Studies

Biological samples collected in this study can be used for animal research. For example, fecal samples from FMT donors and recipients can be orally administered to animal models to study microbiome effects.

### 3. Subsequent Handling of Specimens

Original specimens and derivative materials will be stored for up to 10 years. Specimens may be shipped abroad for analysis or used for research on the gut microbiome. Data generated from this project, including genetic, metagenomic, metabolomic, microbiome, and clinical information, will have all personal identifiers removed (de-identified) and stored in a secure electronic database, such as the Genotype and Phenotype (dbGaP) database managed by the National Institutes of Health (NIH), the Sequence Read Archive (SRA) at NIH, or academic institutions like the Li Ka Shing Health Sciences Research Institute at The Chinese University of Hong Kong or the Wellcome Sanger Institute. Only qualified researchers with institutional or employer support will have access to these data. These researchers will be required to agree not to attempt re-identification of the donors from genetic information.

#### 9. Withdrawal Procedures

Participants may withdraw from study at any time without affecting their access to standard medical care. No further data or samples will be collected after withdrawal. However, any previously collected samples or data that have been processed or uploaded to the databases cannot be deleted, and data already downloaded by qualified researchers cannot be retrieved.

#### 10. Sample Size

The study includes 50 UC recipients for FMT from Bai donors and 50 UC recipients for FMT from Han donors, totaling 100 participants.

#### 11. Statistical Analysis

Continuous variables will be expressed as means (SD) and compared between groups using unpaired t-tests. Categorical variables will be compared using the chi-square test or Fisher's exact test. A modified intent-to-treat analysis will include all participants who have received at least one FMT treatment. Participants requiring additional treatment, violating the study protocol, failing to discontinue corticosteroids by week 12, or discontinuing the study for any reason will be considered treatment failures. Per-protocol analysis will include participants who completed the 12-week blind treatment course without protocol violations. Missing data were handled using complete-case analysis in the primary analysis. A two-sided p-value of <0.05 will be considered statistically significant. Safety data will be summarized using descriptive statistics. All statistical analyses will be performed using R (4.0.5).

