## **5. Assessment Schedule (Table 2)**

### **1. Screening and Group Assignment Visit (-21 Days to Day 0)**

For all consenting patients, baseline demographic and clinical information was collected prior to group assignment, including: Age, gender, and smoking status (current smoker, former smoker, or non-smoker).

- (1) Use of nonsteroidal anti-inflammatory drugs (NSAIDs) or other anticoagulants.
- (2) Use of proton pump inhibitors (PPIs), H2 receptor blockers (H2RB), or other antacids.
- (3) Presence of primary sclerosing cholangitis (PSC).
- (4) History of appendectomy.
- (5) Duration and severity of ulcerative colitis (UC).
- (6) Current treatments and medications.
- (7) Self-reported medication adherence.

Eligible participants were then randomly allocated in a 1:1 ratio to two parallel groups to receive FMT from either a Han donor or a Bai donor.

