## **7. Randomization, Blinding, and Treatment Protocols:**

### **1. Randomization:**

Randomization codes will be computer-generated. Subjects will be randomized according to the sequence of these codes.

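### Clinical outcomes are compared only by unadjusted tests, although baseline MES and oral steroid use, both recorded before assignment, enter the primary endpoint

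*Combined protocol and SAP*

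**What the plan says.** Section 11 (Statistical Analysis) gives two rules for comparing the arms. The first is "Continuous variables will be expressed as means (SD) and compared between groups using unpaired t-tests". The second is "Categorical variables will be compared using the chi-square test or Fisher's exact test", and it governs the binary primary and the three binary clinical secondaries in section 3. The significance rule is "A two-sided p-value of <0.05 will be considered statistically significant". The section names no covariate, regression model, adjusted sensitivity analysis, effect estimate or confidence interval.

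Patients are "randomly allocated in a 1:1 ratio to two parallel groups" (Screening and Group Assignment Visit). Section 7 adds that codes are computer-generated and "Subjects will be randomized according to the sequence of these codes". No stratification factor is mentioned.

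The primary outcome (section 3) requires a total Mayo of 2 or less, no sub-score above 1, freedom from steroids, and "at least a 1 point reduction from baseline in the endoscopy sub-score (MES"). Entry allows total Mayo 4-10 with an endoscopic score of at least 1. Low-dose oral prednisone is permitted at entry with a taper (section 4, Permitted Medications). Under section 11, a patient not off corticosteroids by week 12 counts as a treatment failure.

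The relevant baseline data are collected. The pre-assignment list includes "Duration and severity of ulcerative colitis (UC") and current medication, and the sample collection table marks Mayo with MES at screening.

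**The concern.** Two baseline variables enter the primary endpoint by definition. Baseline MES sets the target: a patient entering at MES 1 must reach 0, while one entering at MES 2 or 3 must reach 1 or less. Baseline oral steroid use adds a route to failure that other patients do not start with. If the arms differ by chance on either variable, the crude difference in remission partly reflects that. Neither the described randomization nor the planned analysis deals with it, although the data are in hand.

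At stake are some precision in a small trial and the accuracy of the estimate given the imbalance that actually occurs. There is also a procedural risk. Investigators know the allocation (section 7), so a decision to adjust that is made after an imbalance has been seen would be hard to defend.

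**Working it through.** **The plan's own figure.** Section 10 gives "50 UC recipients for FMT from Han donors, totaling 100 participants", and 50 + 50 = 100 agrees. No rates, effect size or power are stated, so nothing else can be reproduced. Section 5 plans 30 completers per arm, so both 50 and 30 are used below. All rates, prevalences and covariate strengths are assumptions.

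**MES hurdle, from the definitions.**
- Entry MES 1: must reach 0, a drop of 1.
- Entry MES 2: must reach 1 or less, a drop of at least 1.
- Entry MES 3: must reach 1 or less, a drop of at least 2.

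**Chance imbalance.** Assume 30% enter at MES 1. The 95% limit for the difference in that share between arms is 1.96 × √(2 × 0.3 × 0.7 / n):
- n = 50: 1.96 × √0.0084 = 0.18, or 18 points
- n = 30: 1.96 × √0.014 = 0.23, or 23 points

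Exact (hypergeometric) probabilities of imbalance in a binary factor with prevalence 30-50%:

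| Difference between arms | 50 per arm | 30 per arm |
|---|---|---|
| 10 points or more | 28-32% | 40-44% |
| 20 points or more | 5-7% | 16-20% |

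**Effect on the estimate.** If remission differs by 20 points between MES groups, an 18-point imbalance shifts the crude difference by 0.18 × 0.20 = 0.036, or 3.6 points. At 30% v 50% with 50 per arm, the standard error is √((0.3 × 0.7 + 0.5 × 0.5) / 50) = √0.0092 = 0.096. The shift is therefore 3.6 / 9.6 = 0.375 standard errors.

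**Power for the binary primary.** There were 3,000 simulated trials per setting, at 30% v 50%. The unadjusted two-proportion test was compared with a logistic model on arm, total Mayo, MES (two levels) and steroid use.

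| Outcome variance explained by covariates | 50/arm: unadjusted | 50/arm: adjusted | 30/arm: unadjusted | 30/arm: adjusted |
|---|---|---|---|---|
| 0% | 53.8% | 52.0% | 34.8% | 34.7% |
| 7% | 54.0% | 56.2% | 34.3% | 35.8% |
| 14% | 53.5% | 60.0% | 34.0% | 38.7% |
| 21% | 54.9% | 63.5% | 34.6% | 41.2% |

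- At 50 per arm, the change runs from 52.0 - 53.8 = -1.8 points to 63.5 - 54.9 = +8.6 points.
- The variance of the adjusted risk difference relative to the crude one is 1.03, 0.97, 0.89 and 0.81 in the same order (50 per arm).
- With no treatment effect, the unadjusted test rejected in 4.7-5.5% of trials, so it holds its nominal level.
- The model used three covariates. Two may explain less, and the gain would then be smaller.

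**Room for covariates.** At 30% v 50%, 30 per arm gives 9 + 15 = 24 events. That is 24 / 3 = 8 per parameter with arm, MES (one term) and steroid use, and 24 / 4 = 6 if total Mayo is added. At 50 per arm there are 15 + 25 = 40 events, or about 13 and 10 per parameter.

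**The case against.** The strongest reply is that nothing here is an error. Randomization makes the unadjusted test valid, its confidence interval already allows for random imbalance, and the trial calls itself a pilot. A near-worst-case imbalance moves the estimate by less than 0.4 standard errors, and adjusting for covariates that are not prognostic costs a little power. All of this stands, so the point is an efficiency improvement.

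The direction of any MES effect is also open. MES 1 patients must reach 0 but may be milder overall. A split of MES 1 v 2-3 pools unequal hurdles, since MES 3 needs a two-point drop. These objections bear on how MES is coded more than on whether to adjust for it.

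A reader might infer four stronger claims, which the documents do not support:
- *Every outcome is analysed unadjusted.* Section 8 assigns other methods to the microbiome comparisons, including DB-RDA for clinical factors. Five of the eight secondary outcomes concern the microbiota.
- *Baseline total Mayo drives the primary by definition.* The threshold of 2 is absolute, so baseline total Mayo is only a likely prognostic factor there. It enters by definition in the secondary clinical response.
- *Adjustment is worth a third more patients.* That figure is 1 / (1 - 0.5²) = 1.33, for a continuous outcome with an assumed baseline correlation of 0.5. The clinical outcomes listed in section 3 are all binary, and calprotectin appears only as an assay.
- *Recipient ethnicity belongs in the model.* The background discusses donor differences and diet. It does not discuss matching donor to recipient.

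**Conclusion.** The concern holds for the clinical outcomes, including the primary. They are compared without adjustment, under randomization with no described stratification, although two collected baseline variables enter the primary by definition or through the failure rule. The planned test is valid. The loss is modest precision and uncorrected chance imbalance.

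Under assumed rates of 30% v 50%, adjustment takes power at 50 per arm from about 54% to 52-64%, and at 30 per arm from about 34-35% to 35-41%. Where the trial would fall in those ranges depends on how prognostic the covariates are, which the documents do not say. The change should be made because it is nearly free. It is not a condition for the trial's validity.

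**What to change.** Before any analysis by arm, add to section 11:
- **Primary and binary clinical secondaries:** logistic regression (Firth-penalised if events are sparse) with arm, baseline MES and baseline oral steroid use (yes/no). Add total Mayo only if events allow. State the MES coding in advance; three levels respect the unequal hurdles but cost one more parameter. Report a standardised risk difference with 95% CI, and keep Fisher's exact test as a sensitivity analysis.
- **Calprotectin or Mayo, if analysed as continuous:** ANCOVA with the baseline value as covariate, on the log scale for calprotectin, in place of the raw t-test.
- **Timing of Mayo:** first reconcile when it is assessed. Section 3 says week 12, the treatment and follow-up text places the second colonoscopy at weeks 8-12, and the sample collection table, as extracted, marks week 8 and not week 12. The table may have been damaged in extraction.

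The cost is SAP wording, since every covariate is already recorded. The downsides are a slight precision loss if the covariates are not prognostic and a limit on their number when events are few.

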Our team's high-quality research findings indicate that the gut microbiota of populations in Yunnan's ethnic minority regions exhibits significantly higher diversity and regional specificity compared to urban populations. This has potential value in enhancing FMT efficacy. Previous studies [12] revealed ethnic and regional differences in IBD prevalence in Yunnan Province, with lower rates among the Dai, Bai, and Miao ethnic groups compared to the Han population. An analysis of contributing factors highlighted the protective role of traditional ethnic diets, which increase gut microbial and viral diversity and probiotics content, thereby reducing UC prevalence. Based on this, the differences between donors in FMT may affect treatment outcomes, emphasizing the importance of identifying "high-quality" donors who maximize efficacy and minimize adverse reactions.

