### **2. Objectives:**

To investigate the impact of different donors (Han and Bai ethnic donors) on the efficacy of FMT in treating UC and identify "high-quality" donors.

To isolate and culture key bacterial strains from Bai ethnic donors that contribute to their therapeutic effect.

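### The clinical analysis has no donor term and the number of donors is not stated; if donors are shared among recipients, the false-positive rate for a general Han-versus-Bai claim can exceed 5%.

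*Combined protocol and SAP*

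**What the plan says.** The first objective (section 2) is to study the "impact of different donors (Han and Bai ethnic donors) on the efficacy of FMT" and to identify high-quality donors. The Background (section 1) gives the reason: "the differences between donors in FMT may affect treatment outcomes".

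Under Study Design (section 4), "Patients will be randomized to either the Han donor or the Bai donor and followed up for a 12-week period". Section 10 gives the size: "The study includes 50 UC recipients for FMT from Bai donors and 50 UC recipients for FMT from Han donors, totaling 100 participants". It reports no power calculation, effect size or intraclass correlation (ICC). The Groups table in section 5 plans 50 enrolled and 30 completing 12 weeks in each arm.

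For the clinical outcomes, section 11 states: "Categorical variables will be compared using the chi-square test" or Fisher's exact test. Continuous variables are "compared between groups using unpaired t-tests". The criterion is: "A two-sided p-value of <0.05 will be considered statistically significant". There is no donor term, random effect or cluster adjustment.

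The plan does not say how many donors supply each arm, whether stool is pooled, whether a recipient's three infusions share a donor, or how donors are matched to recipients. Donor is a factor only in the microbiome and metabolomics comparisons of section 8.

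**The concern.** The treatment being compared is donor stool. If some donors work better than others, as the rationale supposes, recipients of the same donor share part of their outcome. A patient-level test then counts each of them as a separate piece of evidence about ethnicity, when part of what they show concerns one person's stool.

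The standard error is then too small for any statement about Han and Bai donors in general. One unusually good or poor donor could produce a significant ethnicity effect. If donor identity is not recorded for each infusion, this cannot be repaired after the trial.

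**Working it through.** **Inputs from the plan.** Two-sided 5% level and patient-level tests (section 11); 50 recipients per arm (section 10); 30 planned completers per arm (section 5). Both sizes are used because section 11 mentions counting discontinuations as failures and also complete-case analysis.

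**Inputs not in the plan, assumed here.** Remission rate 0.30 (0.20 and 0.40 give similar results); ICC for donor 0.05 and 0.10, with 0 and 0.01 for comparison; *m* donors per arm, with recipients spread nearly evenly and one donor per recipient.

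**The plan's own figure.** The total of 100 cannot be reproduced, as no rate, effect or power is given. Only simple arithmetic checks: 50 + 50 = 100, and 30/(1 − 0.40) = 50. The 5% level does hold for independent patients: with ICC 0 and 50 per arm, the simulated rejection rate is 0.050–0.052 for the uncorrected chi-square and 0.028–0.032 for Fisher or the Yates-corrected chi-square.

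**Formula.** Design effect DE = 1 + (50/*m* − 1) × ICC. Approximate type I error = 2 × [1 − Φ(1.96/√DE)].

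- *m* = 2, ICC 0.05: DE = 1 + 24 × 0.05 = 2.20; error 0.186.
- *m* = 2, ICC 0.10: DE = 1 + 24 × 0.10 = 3.40; error 0.288.
- *m* = 5, ICC 0.05: DE = 1 + 9 × 0.05 = 1.45; error 0.104.
- *m* = 5, ICC 0.10: DE = 1 + 9 × 0.10 = 1.90; error 0.155.

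**Simulation.** Beta-binomial outcomes, no ethnicity effect, 200,000 trials per cell, 50 per arm. Each cell gives uncorrected chi-square, with Fisher/Yates in brackets.

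| Donors per arm | ICC 0.05 | ICC 0.10 |
|---|---|---|
| 1 | 0.305 (0.255) | 0.447 (0.394) |
| 2 | 0.190 (0.147) | 0.299 (0.249) |
| 5 | 0.105 (0.073) | 0.158 (0.118) |
| 10 | 0.073 (0.048) | 0.098 (0.068) |
| 25 | 0.055 (0.034) | 0.061 (0.039) |

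With a different donor for each recipient (*m* = 50) the rate at ICC 0.05 is 0.050 (0.031). At ICC 0.01 it is 0.109 (0.077) for one donor per arm and 0.061 (0.038) for five.

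**With 30 completers per arm.** Five donors give 0.078 (0.047) at ICC 0.05 and 0.109 (0.069) at ICC 0.10. Ten donors give 0.061 (0.034) and 0.072 (0.043). Two donors still give 0.133 (0.089) and 0.213 (0.156).

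**Does accounting for donor restore the level?** A t-test on donor proportions with 2(*m* − 1) degrees of freedom (100,000 trials per cell, 50 per arm) rejects in 0.043–0.055 of null trials for *m* = 2 to 25 and ICC 0.05–0.20. With one donor per arm it has no degrees of freedom and cannot be computed.

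**The case against.** The strongest reply is that the inflation rests on two unknowns. It needs shared donors and an ICC above zero, and the documents give neither a donor count nor an ICC. A reader might infer that recipients are certainly clustered by donor and that the error rate certainly exceeds 5%. The text does not support that: 10 donors per arm at ICC 0.05 with Fisher's test, which section 11 allows, gives 0.048. This part of the reply stands, and the point is therefore conditional. Sharing is still likely, though this is inference: avoiding it would need 50 donors per arm, each clearing 49 numbered exclusions, and nothing commits to that.

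A reader might also infer one donor per arm from the singular in Study Design. The Objectives and Sample Size sections use the plural, so this is a case to rule out, not an established fact.

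Two further inferences go too far. Strain culture is a parallel objective and is not made conditional on a significant result. Nor is donor ignored throughout, since section 8 compares donors in the omics work; the gap is in the clinical outcomes.

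If a recipient's infusions come from several donors, the simple design-effect formula no longer applies, so the figures are illustrative for that case.

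Finally, this is a pilot, and comparing only the donors actually used needs no random effect. That is true. But the Background argues from differences between ethnic populations and section 11 sets a significance threshold, so a general ethnicity claim is the natural reading.

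**Conclusion.** The point holds in conditional form. The planned clinical tests ignore donor while the rationale expects donors to differ. If donors are shared, the false-positive rate for a general Han-versus-Bai claim can exceed 5%. At ICC 0.05–0.10, rate 0.30 and 50 per arm, it is about 19–30% with 2 donors per arm and 10–16% with 5 (uncorrected chi-square), or 15–25% and 7–12% with Fisher or Yates.

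With 10 or more donors per arm, or a small ICC and several donors, the excess is small or absent. Analysing 30 completers per arm reduces it, to little or nothing with 5 donors at ICC 0.05 (7.8%, or 4.7% with Fisher/Yates), but does not remove it with 2. With one donor per arm, ethnicity and the individual donor are completely confounded. The ICCs, rates and donor numbers are all assumptions.

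**What to change.** 1. State the number of donors per arm, whether stool is pooled, and the rule assigning donors to recipients. State whether a recipient's three infusions come from one donor; the analysis change does not require that they do.
2. Record donor ID for every infusion.
3. Account for donor in the primary analysis: a donor random effect or, when donors are few, a donor-level comparison with donor-based degrees of freedom.
4. Report remission by donor with intervals. This also serves the aim of identifying high-quality donors.
5. If an arm has only one or two donors, limit the conclusion to those donors and make no claim about ethnicity.

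Most of this is wording, plus use of an identity that section 7 says preparation staff can already access. The real cost is precision. For an assumed 30% versus 50% at ICC 0.10, the donor-level test has power 0.11, 0.18, 0.27, 0.38 and 0.49 with 2, 3, 5, 10 and 25 donors per arm, against 0.53 if 50 patients per arm were independent. Effective sample size per arm with 2 donors is 50/3.40 = 14.7. An ethnicity claim therefore depends on the number of donors as well as the number of recipients, and intervals will be wider.
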